Selective efficacy and health outcomes analyses will be performed for Combined Periods 2 and 3 for the ITT population who are randomized to ixekizumab at Week 0 (Visit 2). These analyses include the primary endpoint, all major secondary endpoints, as well as BASDAI50, ASDAS inactive disease, ASDAS clinically important improvement and major improvement.

Unless otherwise specified, Combined Periods 2 and 3 starts at the first injection of study treatment at Week 0 (Visit 2) and ends on the date of Week 52 (Visit 15) or the ETV (between Weeks 0 and 52).

For the efficacy and health outcomes analyses, baseline is defined as the last available value before the first injection in Period 2 and, in most cases, will be the value recorded at Week 0 (Visit 2). For efficacy measures, if the patient does not take any injection, the last available value on or before randomization date will be used.

The number and percentage of patients achieving a categorical response (for example, ASAS40) will be summarized by treatment group for all scheduled visits (NRI), including Week 52 (Visit 15).

Continuous measure score and change from baseline will be summarized by treatment group at all scheduled visits, including Week 52 (Visit 15) using descriptive statistics (n, mean, SD, median, minimum, and maximum). Missing data will be imputed using mBOCF method (Section 6.3.2).

Selected safety analyses will be performed for Combined Periods 2 and 3 for the Safety Population who are randomized to ixekizumab at Week 0 (Visit 2).

For the above safety analyses, baseline will be defined as the last available value before the first injection at Week 0. In most cases, this will be the measure recorded at Week 0 (Visit 2). For TEAEs, baseline is defined as the time from Visit 1 to the date/time of the first injection.

Additional categorical safety analyses will be conducted in the All Ixekizumab Exposures Safety Population (defined in Section 6.1.5), for each patient, and will include only periods in which ixekizumab is administered. Exposure-adjusted incidence rates of AEs during Week 0-52 timeframe will be provided. For these safety analyses, baseline is defined as follows:

- If ixekizumab is dispensed at Week 0, baseline will be defined as the last available value before the first injection at Week 0. In most cases, this will be the measure recorded at Week 0 (Visit 2). For TEAEs, baseline is defined as the time from Visit 1 to the date/time of the first injection.

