6.1.5. Analysis Populations

The following major analysis populations will be used (additional analysis populations for specific analysis will be defined in the corresponding analysis section):

Intent-to-Treat Population (ITT Population): Unless otherwise specified, efficacy and health outcomes analyses for Period 2 will be conducted on the ITT Population, defined as all randomized patients, even if the patient does not take the assigned treatment, does not receive the correct treatment, or otherwise does not follow the protocol. Patients will be analyzed according to the treatment to which they were assigned.

Per-Protocol Set (PPS): In addition, the primary efficacy analysis will be repeated using the PPS, which is defined as all randomized patients who do not have a subset of important protocol deviations that impact the primary efficacy endpoint (Section 6.14). For example, patients who are not compliant with therapy during the double-blind period will be excluded from the PPS. Compliance with therapy is defined to be missing no more than 20% of expected doses, not missing 2 consecutive doses (all injections in an injection week are counted as 1 dose), and not have any occurrence of over-dosing (that is, took more injections at the same time point than specified in the protocol) during Period 2.

Patients will be analyzed according to the treatment to which they were assigned.

Safety Population: Safety analyses for Period 2 will be conducted on the Safety Population, defined as all randomized patients who received at least 1 dose of study treatment. Patients will be analyzed according to the treatment to which they were assigned in that period.

Extended Treatment Period Population: Efficacy, health outcomes, and safety analyses for Period 3 will be conducted on the Extended Treatment Period Population, defined as all patients who received at least 1 dose of ixekizumab treatment during Period 3.

All Ixekizumab Exposures Safety Population: Safety analyses for combined Blinded Treatment Dosing Period and Extended Treatment Period will be conducted on the All Ixekizumab Exposures Safety Population, defined as all patients who received at least 1 dose of ixekizumab during the study. For each patient, only periods in which ixekizumab is administered are included.

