Follow-Up Population: Safety analyses for Period 4 will be conducted on the Follow-Up Population, defined as all randomized patients who received at least 1 dose of study treatment and have entered Period 4. Patients will be analyzed according to the treatment they received before entering the Follow-up Period. [Table RHBW.6.1](#) summarizes the major analysis purposes intended for each analysis population.

[Table RHBW.6.2](#) describes the treatment groups and the comparisons for each study period and analysis population.

Table RHBW.6.1. Major Analysis Purposes Intended for Each Analysis Population

	ITT Population	Per-Protocol Set	Safety Population	Extended Treatment Period Population	ITT Safety Population Who are Initially Randomized to Ixekizumab at Week 0	All Ixekizumab Exposures Safety Population	Follow-Up Population
Disposition	For Period 2			For Period 3			For Period 4
Baseline Characteristics ^a	For baseline			For baseline			
Treatment Compliance			For Period 2	For Period 3			
Concomitant Medication	For Period 2			For Period 3			
Protocol Deviation	For Period 2			For Period 3			
Exposure			For Period 2	For Period 3	For Combined Periods 2 and 3	For Periods 2 and 3, on ixekizumab treatment only	
Efficacy and Health Outcomes Analyses	For Period 2; For Period 4, only ASAS40	For ASAS40, ASAS20 in Period 2		For Period 3	For primary and major secondary objectives, and selective measures in Combined Periods 2 and 3		
Safety Analyses			For Period 2	For Period 3	For Combined Periods 2 and 3	For Periods 2 and 3, on ixekizumab treatment only	For Period 4
Subgroup Analyses on Efficacy Outcome	For Period 2						
Subgroup Analyses on Safety Outcome			For Period 2				

Abbreviations: ASAS = Assessment of Spondyloarthritis International Society; ITT = intent-to-treat.

^a including patient demographics and other baseline characteristics, historical illness, pre-existing conditions, prespecified medical history, previous therapy.

Table RHBW.6.2. Treatment Groups and Comparisons for Each Study Period and Analysis Population

Study Period	Analysis Population	Treatment Group	Abbreviation	Comparison

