6.12.1. Extent of Exposure

Duration of exposure to study drug will be summarized by treatment group for the Safety Population during the Period 2 and Extension Period Population for Period 3 using descriptive statistics. Exposure for Safety Population who are randomized to ixekizumab at Week 0 and All Ixekizumab Exposures Safety Population during Combined Periods 2 and 3 will be provided.

A by-patient listing of exposure duration with number of active injections and total dose will be provided.

The duration of exposure will be calculated as:

$$\begin{aligned} \text{Duration of exposure (days)} \\ &= \text{Date of last visit (scheduled or unscheduled) in Treatment Period} \\ &\quad - \text{Date of first dose in Treatment Period} + 1 \end{aligned}$$

The number and percentage of patients in each of the following categories will be included in the summaries:

- >0, ≥7 days, ≥14 days, ≥30 days, ≥60 days, ≥90 days, ≥120 days, (for period 3 add: ≥150 days, ≥183 days, ≥210 day and ≥273 days). Note that patients may be included in more than 1 category.
- >0 to <7 days, ≥7 to <14 days, ≥14 to <30 days, ≥30 to <60 days, ≥60 to <90 days, ≥90 to <120 days, ≥120 days (for Period 3, change ≥120 days to ≥120 to <150 days, add ≥150 to <183 days, ≥183 to <210 days, ≥210 to <273 days, and ≥273 days)

The summaries will also include the following information:

- Total exposure in patient years, calculated as:

$$\begin{aligned} \text{Total exposure in patient years} \\ &= \frac{\text{Sum of duration of exposures for all patients in treatment group}}{365.25} \end{aligned}$$

- Mean and median total dose. Total dose (in mg) is calculated by the number of active injections taken during the treatment period multiplied by dose. For those randomized to

ixekizumab 80 mg (Q2W or Q4W), the total dose (in mg) taken during Period 2 or 3 will be calculated as follows:

Total Period 2 or 3 dose for patients on ixekizumab 80 mg Q2W
= Total number of active injections (including loading doses, if any) received in Period 2 or 3
× 80

Total Period 2 or 3 dose for patients on ixekizumab 80 mg Q4W
= Total number of active injections (including loading doses, if any) received in Period 2 or 3
× 80

Total number of injections received will be derived using the response to the question “Was dose administered?” on the *Exposure as Collected* eCRF page and the actual dose description from IWRS study drug dispense dataset.

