Sub-Category: Excluded Con-meds	Exclude from PPS (Excluded Con-meds refers to clinically meaningful change in con-meds [Appendix 13] when occurred during Period 2 and prescribed for primary study condition) Excluded Con-meds in Period 3 refer to the lists in Appendix 13 .	Monitor and Stats
Sub-Category: Lab/Imaging Criteria		
Missing imaging as per protocol schedule of events	Do not exclude from PPS	Monitor
Missing lab chemistry and hematology: missing baseline or not having at least 1 postbaseline	Do not exclude from PPS	Stats
Sub-Category: Other		
Missing QIDS total score: missing baseline or any scheduled visit before discontinuation visit	Do not exclude from PPS	Stats
Missing Columbia scale at any visit except V1	Do not exclude from PPS	Monitor and Stats
Missing ASAS components for ASAS40 derivation: not having Week 16 measurement for patients who have completed Week 16	Do not exclude from PPS. Note: if missing ASAS components lead to missing ASAS40, such patient will be treated as nonresponder for the Week 16 ITT analyses	Stats
Had unqualified site personnel perform clinical safety and/or efficacy assessments	Do not exclude from PPS	Monitor
Category: Investigational Product		
Sub-Category: Treatment Assignment/Randomization Error		
Took incorrect study medication	Do not exclude from PPS. Analyze ‘As randomized’ or ‘As assigned’.	Monitor and Stats
Sub-Category: Compliance	Exclude from PPS when occurred during Period 2	Stats

Important Protocol Deviation Category/Subcategory/Study Specific	Action for PPS Analysis	Source to Identify Protocol Deviation ^a
Sub-Category: Patient took medication not fit for use	Do not exclude from PPS	Monitor
Sub-Category: Unblinding	Exclude from PPS	Monitor
Sub-Category: Other		
Randomized but did not take any study medication	Exclude from PPS	Stats
Category: Safety		
Sub-Category: SAEs	Do not exclude from PPS	Monitor
Category: Informed Consent		
Sub-Category: Informed Consent not Obtained/Missing/Late	Exclude from PPS	Monitor and Stats
Subcategory: Improper Informed Consent	Do not exclude from PPS	Monitor
Category: Administrative/Oversight		
Sub-Category: Reg/Ethic Approvals	Exclude from PPS	Monitor
Sub-Category: Other		
Enrolled in a site with significant GCP non-compliance issue	Exclude from PPS	Monitor

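### Period 2 safety is compared only by assigned treatment; no by-received table is planned if a patient is given the wrong study drug

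*SAP*

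**What the plan says.** SAP 6.1.5 admits to the Period 2 Safety Population every randomized patient with at least one dose of study treatment, and then sets the grouping: "Patients will be analyzed according to the treatment to which they were assigned in that period". Protocol 9.2.4 carries the same rule.

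Two other safety sets in SAP 6.1.5 work by receipt:
- The All Ixekizumab Exposures Safety Population is "defined as all patients who received at least 1 dose of ixekizumab during the study", and "For each patient, only periods in which ixekizumab is administered are included".
- For the Follow-Up Population, "Patients will be analyzed according to the treatment they received before entering the Follow-up Period".

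The important-deviation table in SAP 6.14 has an entry "Took incorrect study medication". Its stated action concerns the per-protocol set: the patient is kept and analysed as randomized or assigned.

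SAP 6.12.1 derives the number of injections received from the administration record together with "the actual dose description from IWRS study drug dispense dataset". The data needed to identify what a patient actually received are therefore already in use.

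**The concern.** A safety comparison asks what exposure to the drug does. Under the assigned-treatment rule, a placebo patient who receives ixekizumab in error stays in the placebo column, together with every event that follows. According to Table RHBW.6.2, Period 2 is the only period in which ixekizumab safety is compared with placebo; the later and combined periods have no between-group comparisons. If the drug caused the event, the case moves from the treated side to the control side and the difference shrinks, which is the non-conservative direction for safety. The reverse error, placebo given to an ixekizumab patient, dilutes the ixekizumab rate.

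This matters most for adverse events of special interest, where a table may rest on a handful of cases. The plan foresees wrong-drug dosing but prescribes no safety analysis that reflects it.

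**Working it through.** The plan states no figure on this point, so the check is a comparison of texts followed by an illustration.

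**1. Where the same event would be counted.** Take a placebo-assigned patient given ixekizumab in error during Period 2, with an event afterwards.
- *Period 2 Safety Population (SAP 6.1.5):* placebo, by the assignment rule.
- *Patients initially randomized to ixekizumab, combined Periods 2 and 3 (Table RHBW.6.2):* not included. This set follows the Period 2 grouping.
- *All Ixekizumab Exposures set, error at Week 0:* ixekizumab. The patient qualifies by receipt, and SAP 6.1.3 supplies a baseline: "If ixekizumab is dispensed at Week 0, baseline will be defined as the last available value before the first injection at Week 0".
- *All Ixekizumab Exposures set, error after Week 0:* unclear. Read literally, 6.1.5 counts Period 2 as a period in which ixekizumab was given. The 6.1.3 baseline rule for a patient dispensed placebo at Week 0 instead assumes that the first ixekizumab injection is at Visit 8. On that baseline, the Period 2 event would not be treatment-emergent.
- *Column in the exposure set:* not stated. The regimens shown are Q2W and Q4W, and one stray 80 mg syringe belongs to neither.

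**2. Illustrative size.** The 100 patients per arm come from the protocol synopsis. Event counts and numbers of errors are assumptions. Each mis-dosed placebo patient is assumed to have the event. SAP 6.1.1 specifies Fisher's exact test. With k such patients, a ixekizumab events and b placebo events among the others:
- by assigned: a/100 versus (b+k)/100
- by received: (a+k)/(100+k) versus b/(100−k)

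| k | a, b | By assigned | p | By received | p |
|---|---|---|---|---|---|
| 1 | 3, 0 | 3/100 vs 1/100 | 0.621 | 4/101 vs 0/99 | 0.121 |
| 1 | 5, 0 | 5/100 vs 1/100 | 0.212 | 6/101 vs 0/99 | 0.029 |
| 3 | 3, 0 | 3/100 vs 3/100 | 1.000 | 6/103 vs 0/97 | 0.029 |

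One event in 100 patients is 1 percentage point. With k=0 the two classifications are identical.

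**3. The same illustration with the mis-dosed patient under Total Ixekizumab.** With 2 × 100 = 200 ixekizumab patients, 2 × 5 = 10 events among them and k=1: by assigned 10/200 versus 1/100, p=0.107; by received 11/201 versus 0/99, p=0.018. If the patient only leaves the placebo column and joins neither regimen, the single-regimen comparison is 5/100 versus 0/99, p=0.059, against 0.212 by assignment.

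**The case against.** The rule is explicit, and protocol and SAP agree on it. A reader might infer an error or a protocol–SAP conflict; the documents do not support that. It is an analysis choice, and the deviation table shows that wrong-drug dosing was considered, though only for the per-protocol set.

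A reader might also infer that the Period 2 and Weeks 0–52 safety tables contradict each other in general. They do not. The combined-period set of patients initially randomized to ixekizumab matches the Period 2 grouping, and the exposure set differs by design because it includes placebo patients' ixekizumab time after Week 16. Opposite attribution of one event is clear only for a Week 0 error.

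Such cases would be traceable. Important deviations are summarized by arm and listed by patient (SAP 6.14). By-patient listings also cover drug dispensed with lot number (6.8), active injections and total dose (6.12.1), and all adverse events (6.12.2). Sites confirm each package number in the IWRS (SAP 5.2), which should keep errors few.

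The illustration is conditional as well. At an assumed 1% event risk, one to three mis-dosed patients produce a case with probability 1 − 0.99^k, about 1% to 3%. The 5 versus 0 starting point is already near the threshold (p=0.059). A single case moving from one column to the other can reverse the direction of a count, but 1/100 versus 0/100 and 0/100 versus 1/100 both give p=1.

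All of this stands, and it limits the point. It does not replace a planned comparison: listings let someone find the case but do not say how the controlled table should read once it is found.

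**Conclusion.** The concern holds in a limited form. Period 2 safety is compared only by assigned treatment, and no by-received comparison is planned for an event the SAP itself lists. If a placebo-assigned patient is given ixekizumab in error, later drug-caused events fall in the control column and bias the comparison toward no difference. The exposure set would count a Week 0 error as ixekizumab, while its handling of a later error is unsettled.

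The effect is nil without dosing errors and about one percentage point per affected event at 100 per arm. It could matter for a sparse event table but hardly for common events. This rests on two assumptions: that at least one wrong-drug error occurs, for which the documents give no rate, and that the event is related to the drug. The existing tables are not wrong; a supplementary rule is missing.

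**What to change.** Add to SAP 6.1.5: if any patient receives the wrong study drug in Period 2, the TEAE, SAE and AESI comparisons are also presented by treatment actually received, derived from the administration log and IWRS dispense data already used in 6.12.1. Specify that:
- a placebo-assigned patient's events count as ixekizumab only from the first ixekizumab injection, so earlier events stay under placebo;
- such a patient appears under Total Ixekizumab and is not forced into Q2W or Q4W;
- each such patient is footnoted;
- the denominator rule is stated, because the patient contributes time to both columns, and Total Ixekizumab versus placebo is added for this table, since Table RHBW.6.2 lists only the regimen-level and overall comparisons.

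Moving the whole patient to ixekizumab would be worse, because it would carry over events that preceded the exposure. Choosing a regimen by counting active injections would not work either, because every active syringe is 80 mg in both regimens.

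In SAP 6.1.3, define the exposure-population baseline by the first actual ixekizumab injection. Keep ITT efficacy and the assigned-treatment safety tables.

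The cost is one derived variable, a few sentences and, only if an error occurs, an extra set of tables whose groups may differ from the randomized groups by a few patients. Version 3 of the SAP was approved before first unblinding in June 2018 and Version 4 followed in February 2019. An addition now should therefore be labelled as supplementary and made after the Week 16 unblinding.

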6.2. Adjustments for Covariates

The countries will be categorized into geographic regions for statistical analysis (Table RHBW.6.3). Unless otherwise specified, the statistical analysis models will adjust for geographic region, baseline CRP status (nonelevated or elevated), and number of prior TNF inhibitors used (1 or 2).

Below are the initial country allocations.

Table RHBW.6.3. Geographic Regions for Statistical Analysis

Geographic Region	Country or Countries
Non-Europe	United States, Canada, Mexico, Korea, Argentina, Israel, Brazil
Europe	Finland, France, Poland, Germany, Italy, Spain, UK, The Netherlands

In general, when an MMRM is to be used for analyses, baseline value and baseline-by-visit interactions will be included as covariates; when an ANCOVA is to be used for analyses, baseline value will be included as a covariate.

6.3. Handling of Dropouts or Missing Data

In accordance with precedent set with other Phase 3 axSpA trials (van der Heijde et al. 2006; Inman et al. 2008), the following methods for imputation of missing data will be used:

6.3.1. Nonresponder Imputation

Analysis of categorical efficacy and health outcomes variables will be assessed based on treatment success/failure. This approach yields results numerically identical to NRI, but it is interpreted differently. Patients will be considered treatment failures if they do not meet the clinical response criteria or have missing clinical response data at the primary analysis time point. Randomized patients without at least 1 postbaseline observation will also be defined as nonresponders for the NRI analysis.

With NRI, as the acronym implies, there is explicit imputation of missing ASAS40 outcomes. With treatment success/failure, discontinuation of study medication is considered a treatment failure because if patients cannot adhere to the medication, they will not have sustained benefit from it. Therefore, every patient will have an observation for treatment success/failure and there will be no missing data for this estimand, and hence inferences will not depend on missing data assumptions. These attributes also apply to other endpoints involving use of NRI.

6.3.2. Modified Baseline Observation Carried Forward

An mBOCF analysis will be performed on continuous efficacy and health outcomes variables in the major and other secondary objectives. For patients discontinuing study drug due to an AE, the baseline observation will be carried forward to the corresponding time point for evaluation. For patients discontinuing study drug for any other reason, the last nonmissing observation before discontinuation will be carried forward to the corresponding time point for evaluation.

Randomized patients without at least 1 postbaseline observation will not be included for evaluation with the exception of patients discontinuing study treatment because of an AE.

6.3.3. Last Observation Carried Forward

An LOCF analysis will be performed on continuous efficacy and health outcomes variables in the major secondary objectives. This approach is identical to the mBOCF approach, with 1 exception: for patients discontinuing study drug because of an AE, the last nonmissing postbaseline observation before discontinuation will be carried forward to the corresponding time point for evaluation. Randomized patients without any postbaseline observation will not be included for evaluation.

6.3.4. Placebo Multiple Imputation

The placebo multiple imputation (pMI) method will be used for the analyses of primary efficacy endpoints ASAS40, major secondary efficacy endpoints ASAS20, and ASDAS change from baseline at Week 16 (Visit 8). [Appendix 1](#) presents the detailed scientific justification of the pMI method.

Placebo multiple imputation assumes that the statistical behavior of drug- and placebo-treated patients after discontinuing study medication becomes that of placebo-treated patients. Multiple imputations (MIs) are used to replace missing outcomes for drug- and placebo-treated patients who discontinued, utilizing multiple draws from the posterior predictive distribution estimated from the placebo arm.

Data are processed sequentially by repeatedly calling SAS® PROC MI to impute missing outcomes at visits $t=1, \dots, T$.

1. *Initialization.* Set $t=0$ (baseline visit).
2. *Iteration.* Set $t=t+1$. Create a dataset combining records from drug- and placebo-treated patients with columns for covariates \mathbf{X} and outcomes at visits $1, \dots, t$ with outcomes for all drug-treated patients set to missing at visit t and set to observed or imputed values at visits $1, \dots, t-1$.
3. *Imputation.* Run Bayesian regression in SAS® PROC MI on this data to impute missing values for visit t using previous outcomes for visits 1 to $t-1$ and baseline covariates. Note that only placebo data will be used to estimate the imputation model since no outcome is available for drug-treated patients at visit t .
4. Replace imputed data for all drug-treated patients at visit t with their observed values, whenever available. If $t < T$, then go to Step 2, otherwise proceed to Step 5. Repeat Steps 1 to 4 m times with different seed values to create m imputed complete datasets.
5. *Analysis.* For each completed dataset, use the model as would have been applied had the data been completed for continuous outcome. For the efficacy endpoints, ASAS20 and ASAS40, the missing binary outcomes will be imputed directly for each patient before fitting into the analysis model. A logistic regression model will be applied.

The final inference on treatment difference is conducted from the multiple datasets using Rubin's combining rules, as implemented in SAS® PROC MI ANALYZE.

Thus, in the effectiveness context, pMI assumes no pharmacological benefit of the drug after dropout but is a more reasonable approach than mBOCF because, unlike BOCF and mBOCF, pMI accounts for uncertainty of imputation, and therefore does not underestimate standard errors and limits bias by taking into account study/placebo effects. In the efficacy context, pMI is a specific form of a missing-not-at-random (MNAR) analysis expected to yield a conservative estimate of efficacy.

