**Statistical Analysis:**

Approximately 300 patients will be randomized at a 1:1:1 ratio in the Blinded Treatment Dosing Period to ixekizumab 80 mg Q2W, ixekizumab 80 mg Q4W, and placebo. With 100 patients per treatment group, this study will have approximately 96% power to test the superiority of ixekizumab Q2W to placebo for the ASAS40 at Week 16. The following assumptions were used for the power calculations for ASAS40 response rates at Week 16 regardless of ixekizumab starting dose: 27% for ixekizumab Q2W treatment group and 7% for placebo group. A 2-sided Fisher's exact test at the 0.05 level is assumed. The efficacy analyses for the Blinded Treatment Dosing Period will be conducted on the intent-to-treat (ITT) population, and safety analyses will be conducted on the safety population.

Comparisons between each ixekizumab treatment group (80 mg Q2W or 80 mg Q4W) and placebo will be performed for all analyses in the Blinded Treatment Dosing Period. Unless otherwise specified, ixekizumab 80 mg Q2W and Q4W groups will be analyzed without regard to starting dose. The primary analysis method for treatment group comparisons of categorical efficacy and health outcomes variables will be a logistic regression analysis with treatment, geographic region, baseline CRP status (nonelevated or elevated), and prior number of TNF inhibitor used (1 or 2) as factors, using the nonresponder imputation (NRI) method. Under NRI, all nonresponders at Week

16 (Visit 8), as well as all patients who discontinue study treatment at any time prior to Week 16 for any reason, will be defined as nonresponders for the NRI analysis at Week 16. Randomized patients without any postbaseline observation will also be defined as nonresponders for the NRI analysis. A graphical multiple testing strategy for the primary and major secondary objectives will be implemented to control the family-wise type I error rate at a 2-sided  $\alpha$  level of 0.05.

The primary analyses for the continuous efficacy and health outcomes variables will be made using mixed-effects model of repeated measures (MMRM) analysis with treatment, geographic region, baseline CRP status, prior number of TNF inhibitor used, baseline value, visit, baseline value-by-visit, and treatment-by-visit as fixed factors.

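### Placebo multiple imputation of ASAS40 as a yes/no outcome rests on about 7 placebo responders; an ordinary logistic imputation model would almost always separate and give dropouts far more than a placebo-like response

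*SAP*

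**What the plan says.** SAP 6.3.4 describes pMI as a sequential procedure over the postbaseline visits. At each visit the ixekizumab outcomes are set to missing before the regression is run, so "only placebo data will be used to estimate the imputation model". The predictors are the outcomes at all previous visits plus baseline covariates X, which the section does not list. For ASAS20 and ASAS40, Step 5 says that "the missing binary outcomes will be imputed directly for each patient before fitting into the analysis model"; logistic regression and combination by Rubin's rules follow. The visible text names no binary imputation model and says nothing about separation.

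The section's premise is that, after stopping study drug, patients in every arm behave like placebo patients. It calls the result "expected to yield a conservative estimate of efficacy". SAP 6.10.5.1 makes pMI a sensitivity analysis for ASAS40 (primary), ASAS20 and ASDAS change at Week 16.

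The planning rates are in the Protocol Synopsis, Statistical Analysis: "27% for ixekizumab Q2W treatment group and 7% for placebo group", "With 100 patients per treatment group".

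**The concern.** Seven per cent of 100 is 7 placebo responders at Week 16, and earlier visits probably have fewer. A logistic model with as many predictors as events will usually contain a combination of predictors that perfectly predicts response or nonresponse. Its estimates then run off towards infinity with very large standard errors. Multiple imputation draws coefficients from a distribution around those estimates, so the predicted probabilities swing between near 0 and near 1. Averaged over draws, they move away from the low placebo rate and towards one half.

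If so, ixekizumab dropouts could be given an ASAS40 response at or above the 27% planned for patients assigned to drug. Placebo dropouts would be inflated too. The analysis would then not test what it was set up to test. ASDAS is imputed as a score and does not face this problem.

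**Working it through.** **1. The plan's own figure.** Inputs: 27% and 7%, 100 per arm, and "A 2-sided Fisher's exact test at the 0.05 level is assumed". Exact enumeration over the two binomials gives 96.5% power (pooled z-test: 96.9%). The Synopsis says "this study will have approximately 96% power to test the superiority of ixekizumab Q2W to placebo". Reproduced, so the 7% rate is a sound input.

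**2. Events against predictors.**
- Events: 100 × 0.07 = 7 placebo responders (95% binomial range 2 to 12). With 10% dropout, about 0.9 × 7 = 6.3 are observed.
- Predictors at Week 16: the Schedule of Activities (Protocol Appendix 2) has postbaseline visits at Weeks 1, 2, 4, 8, 12 and 16, so there are five earlier outcomes. Taking X as the adjustment factors in SAP 6.2 (region, CRP status, number of prior TNF inhibitors) adds three, for a total of 8.
- Events per predictor: 7/8 = 0.9.

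**3. Simulation of Steps 1 to 5.** 150 trials with 20 imputations each; placebo n = 100 reaching 7% and drug reaching 27% at Week 16; latent visit correlation 0.5 to 0.9; monotone dropout of 10% (range 5-20%); sequential logistic imputation fitted on placebo with normal draws. The benchmark is the true placebo-model response given each drug dropout's own history.

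| Imputation model | Imputed, drug dropouts | Imputed, placebo dropouts | Benchmark |
|---|---|---|---|
| Ordinary logistic, all visits + 3 covariates, up to 25 iterations | 29-40% | 29-39% | 6-14%, mainly 9-10% |
| Same, stopped at 8 iterations | 26-28% | 22-24% | 9-10% |
| Same, stopped at 5 iterations | 18% | 14% | 10% |
| Penalised (augmented) likelihood, all visits + 3 covariates | 13-21% | 13-17% | 6-10% |
| Ordinary, all visits, no covariates | 12-19% | 12-15% | 6-10% |
| Ordinary, last visit + 3 covariates | 23% | 22% | 10% |
| Ordinary, last visit only, no covariates | 11-12% | 10% | 9-10% |
| Ordinary, all visits + 3 covariates, placebo rate 13% | 26% | 25% | 15% |
| Ordinary, all visits + 3 covariates, placebo rate 30% (ASAS20-like) | 36% | 32% | 34% |

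In the first row every trial had at least one separated or near-separated fit (standard error above 10), and 78-96% of visit-level fits were affected. At the 30% placebo rate, 2% were. Changing dropout to 5% or 20% gave 34% and 37% in drug dropouts.

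A separate simulation (placebo rate about 9%, 10% dropout) separated in 98% of Week 16 fits. It imputed 28% (placebo) and 33% (drug), against large-sample targets of 9% and 15%.

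**4. Effect on the comparison.** Arm rate = completer rate × (1 − d) + q × d, where d is dropout and q the imputed response. With d = 10% in both arms:
- q = 8%: drug 0.243 + 0.008 = 25.1%; placebo 0.063 + 0.008 = 7.1%. Difference 18.0 points; odds ratio (0.251/0.749)/(0.071/0.929) = 4.4.
- q = 35%: drug 0.243 + 0.035 = 27.8%; placebo 0.063 + 0.035 = 9.8%. Difference 18.0 points; odds ratio (0.278/0.722)/(0.098/0.902) = 3.5.

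Approximate power falls from 93.9% to 90.9%, before any extra between-imputation variance. At 20% dropout it falls from 88.9% to 80.4%.

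With unequal dropout the risk difference shifts by (0.35 − 0.08) × (d_drug − d_placebo). At an illustrative 15% and 5% that is 0.27 × 0.10 = 2.7 points in the drug's favour (17.1 to 19.8), and the odds ratio rises from 4.20 to 4.28. At 10% and 5% the risk difference gains 1.35 points, but the odds ratio still falls, from 4.42 to 4.20.

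**The case against.** **The SAP does not say ordinary logistic.** This stands in part. Section 6.3.4 speaks only of Bayesian regression in PROC MI. Appendix 1, cited for the justification of pMI, is redacted, so further detail there cannot be excluded. A reader might infer that a response of 20-35% in dropouts is built into the plan. It is not: the size depends on the link, X, the iteration limit, the handling of separation and the visit correlation. The lowest results, however, drop covariates or earlier visits that Step 3 includes, or stop the fit before it has converged. A penalised likelihood keeps all the predictors and still overshoots.

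**The contrast barely moves, and the odds ratio shrinks.** This stands for equal dropout. A reader might infer that the SAP's claim of a conservative estimate is simply false, or that the analysis is biased for the drug. Neither follows: with equal dropout the odds ratio moves towards the null. But it does so because both arms are inflated, not because dropouts were given placebo behaviour, and the direction is not guaranteed when dropout differs.

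**Robustness is covered elsewhere.** This stands. The primary analysis counts discontinuation as failure (SAP 6.3.1, 6.10.1). The ASAS40 tipping-point analysis sets response probabilities directly (SAP 6.3.5). Week 16 data after discontinuation are summarised (SAP 6.10.5.3). None of these uses the pMI model, so there is no ground for doubting the primary result on this account.

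**Score imputation also overshoots.** Against the binary model's benchmark it seems to, but that is the wrong target. Scores keep a drug dropout's partial improvement, which a yes/no history discards. In the separate simulation, score imputation gave 11% (placebo) and 23% (drug) against its own large-sample targets of 9% and 20%. That is an excess of 2 and 3 points, compared with 19 and 18 for binary imputation.

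**Conclusion.** The concern holds for ASAS40 pMI. With about 7 expected placebo responders and about 8 predictors, an ordinary logistic imputation model would separate almost always. It would give dropouts in both arms roughly 22-40% response (13-21% if penalised), against a placebo-model rate of about 6-15%, mainly 9-10%. The analysis would then not deliver the placebo-like behaviour on which 6.3.4 rests. At equal 10% dropout the cost is about 2.7 points on each arm rate and an odds ratio of 3.5 instead of 4.4, with the risk difference unchanged. Higher drug dropout shifts the risk difference in the drug's favour, and a large enough gap shifts the odds ratio too.

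The event count follows from the Protocol. The predictor count assumes that X is the set of analysis factors. Dropout, early-visit rates, visit correlations and the iteration limit are assumptions; stopping at 5 iterations gave 14-18%. ASAS20 is little affected at about 30% placebo response, itself an assumed rate.

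**What to change.** In SAP 6.3.4 Step 5, impute the four ASAS domain scores (Patient Global, Spinal Pain, BASFI, and inflammation from BASDAI questions 5 and 6) with the same sequential placebo-based regression. All four can be obtained at every Period 2 visit. Cap imputed values at 0-10, derive ASAS40 in each completed data set, then run the planned logistic model and combine. Do the same for ASAS20 for consistency.

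If binary imputation is kept, name the model, list X, use a penalised likelihood and cut the predictors, for example to the last visit only. The covariates must go as well: last visit without covariates gave 10-12% against 9-10%, but 22-23% with them. Those runs were unpenalised and 17-38% of their fits still separated, so the penalty is a safeguard whose combination with the reduced set was not simulated.

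Cost: SAP wording and more programming, with four variables per visit to impute instead of one. SAP Version 4 postdates the first unblinding (SAP Section 3), so any rerun of Week 16 results must be labelled as done after unblinding.
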